8. WITHDRAWAL FROM TREATMENT, PROCEDURES, AND STUDY

8.1 Subjects' Decision to Withdraw

Subjects have the right to withdraw from the study at any time and for any reason without prejudice to their future medical care by the physician or at the institution.

Subjects (or a legally acceptable representative) can decline to continue receiving investigational product and/or other protocol-required therapies or procedures at any time during the study but continue participation in the study. If this occurs, the investigator is to discuss with the subject the appropriate processes for discontinuation from investigational product or other protocol-required therapies and must discuss with the subject the options for continuation of the Schedule of Assessments ([Table 2](#)) and collection of data, including endpoints and adverse events. The investigator must document the change to the Schedule of Assessments ([Table 2](#)) and the level of follow-up that is agreed to by the subject (eg, in person, by telephone/mail, through family/friends, in correspondence/communication with other physicians, from review of the medical records).

Withdrawal of consent for a study means that the subject does not wish to receive further protocol-required therapies or procedures, and the subject does not wish to or is unable to continue further study participation. Subject data up to withdrawal of consent will be included in the analysis of the study, and where permitted, publically available data can be included after withdrawal of consent. The investigator is to discuss with the subject appropriate procedures for withdrawal from the study.

8.2 Investigator or Sponsor Decision to Withdraw or Terminate Subjects' Participation Prior to Study Completion

The investigator and/or sponsor can decide to withdraw a subject(s) from investigational product and/or other protocol-required therapies, protocol procedures, or the study as a whole at any time prior to study completion.

Subjects may be eligible for continued treatment with Amgen investigational product(s) and/or other protocol-required therapies by a separate protocol or as provided for by the local country's regulatory mechanism, based on parameters consistent with [Section 12.1](#).

8.3 Reasons for Removal From Treatment or Study

8.3.1 Reasons for Removal From Treatment

Reasons for removal from the protocol-required investigational product or procedural assessments may include any of the following:

- subject request
- safety concern (eg, due to an adverse event, ineligibility determined, protocol deviation, non-compliance (eg, procedural or dosing as defined in [Section 6.2.1.1](#)), requirement for alternative therapy, pregnancy)
- decision by sponsor (other than subject request or safety concern)
- death
- lost to follow-up
- clinically relevant disease progression beyond 6 months of treatment, per modified WHO response criteria ([Appendix D](#))
- other protocol-specified criteria ([Section 6.2.1.2](#))

8.3.2 Reasons for Removal From Study

Reasons for removal of a subject from the study are:

- decision by sponsor
- withdrawal of consent from study
- death
- lost to follow-up

9. SAFETY DATA COLLECTION, RECORDING, AND REPORTING

9.1 Adverse Events

9.1.1 Definition of Adverse Events

An adverse event is defined as any untoward medical occurrence in a clinical trial subject. The event does not necessarily have a causal relationship with study treatment.

The investigator is responsible for ensuring that any adverse events observed by the investigator or reported by the subject are recorded in the subject's medical record.

The definition of adverse events includes worsening of a pre-existing medical condition. Worsening indicates that the pre-existing medical condition (eg, diabetes, migraine headaches, gout) has increased in severity, frequency, and/or duration, and/or has an association with a significantly worse outcome. A pre-existing condition that has not worsened during the study or involves an intervention such as elective cosmetic surgery or a medical procedure while on study, is not considered an adverse event.

For situations when an adverse event or serious adverse event is considered to be due to melanoma, report all known signs and symptoms. Death due to disease progression in the absence of signs and symptoms should be reported as the primary tumor type (eg, worsening of melanoma).

Note: The term "disease progression" should not be used to describe the adverse event.

The investigator's clinical judgment is used to determine whether a subject is to be removed from treatment due to an adverse event. In the event a subject, or subject's legally acceptable representative requests to withdraw from protocol-required therapies or the study due to an adverse event, refer to [Section 8.1](#) for additional instructions on the procedures recommended for safe withdrawal from protocol-required therapies or the study.

9.1.2 Definition of Serious Adverse Events

A serious adverse event is defined as an adverse event that meets at least 1 of the following serious criteria:

- fatal
- life threatening (places the subject at immediate risk of death)
- requires in-patient hospitalization or prolongation of existing hospitalization
- results in persistent or significant disability/incapacity
- congenital anomaly/birth defect
- other medically important serious event

An adverse event would meet the criterion of "requires hospitalization", if the event necessitated an admission to a health care facility (eg, overnight stay).

If an investigator considers an event to be clinically important, but it does not meet any of the serious criteria, the event could be classified as a serious adverse event under the criterion of "other medically important serious event". Examples of such events could

include allergic bronchospasm, convulsions, blood dyscrasias, or events that necessitate an emergency room visit, outpatient surgery, or urgent intervention.

9.2 Reporting of Adverse Events

9.2.1 Reporting Procedures for Adverse Events That do not Meet Serious Criteria

The investigator is responsible for ensuring that all adverse events observed by the investigator or reported by the subject that occur after the first dose of talimogene laherparepvec through 30 (+ 7) days after the last dose of talimogene laherparepvec are reported using the applicable eCRF (eg, Adverse Event Summary). **Adverse events deemed by the investigator to be potentially related to talimogene laherparepvec that occur during and after the first dose of talimogene laherparepvec and through the survival follow-up are to be reported.**

The investigator must assign the following adverse event attributes:

- adverse event diagnosis or syndrome(s), if known (if not known, signs or symptoms),
- dates of onset and resolution (if resolved),
- severity (and/or toxicity per protocol),
- assessment of relatedness to talimogene laherparepvec and
- action taken.

The adverse event grading scale used will be the Common Terminology Criteria for Adverse Events (CTCAE), version 3.0. The grading scale used in this study is described in [Appendix A](#). The investigator must assess whether the adverse event is possibly related to talimogene laherparepvec. This relationship is indicated by a “yes” or “no” response to the question: Is there a reasonable possibility that the event may have been caused by administration of investigational product?

The investigator must assess whether the adverse event is possibly related to any study-mandated activity and/or procedure (eg, including any screening procedures). This relationship is indicated by a “yes” or “no” response to the question: “Is there a reasonable possibility that the event may have been caused by a study activity and/or procedure”?

The investigator is responsible for reviewing laboratory test results and determining whether an abnormal value in an individual study subject represents a clinically significant change from the subject’s baseline values. In general, abnormal laboratory findings without clinical significance (based on the investigator’s judgment) are not to be recorded as adverse events. However, laboratory value changes that require treatment

or adjustment in current therapy are considered adverse events. Where applicable, clinical sequelae (not the laboratory abnormality) are to be recorded as the adverse event.

If the severity of an adverse event worsens from the date of onset to the date of resolution, record a single event for each increased level of severity on the Adverse Event Summary eCRF. The investigator is expected to follow reported adverse events until stabilization or reversibility.

9.2.2 Reporting Procedures for Serious Adverse Events

The investigator is responsible for ensuring that all serious adverse events observed by the investigator or reported by the subject that occur after signing of the informed consent through 30 (+ 7) days after the last dose of talimogene laherparepvec are recorded in the subject's medical record and are submitted to Amgen. All serious adverse events must be submitted to Amgen within 24 hours following the investigator's knowledge of the event via the applicable eCRF.

After the protocol-required reporting period defined above, the investigator does not need to actively monitor subjects for serious adverse events. However, if the investigator becomes aware of a serious adverse event after this protocol-required reporting period, the investigator will report the event to Amgen within 24 hours following the investigator's knowledge of the event. Serious adverse events reported outside of the protocol-required reporting period will be captured within the safety database as clinical trial cases for the purposes of expedited reporting.

If the electronic data capture (EDC) system is unavailable to the site staff to report the serious adverse event, the information is to be reported to Amgen via an electronic Serious Adverse Event (eSAE) Contingency Report Form within 24 hours of the investigator's knowledge of the event. See [Appendix B](#) for a sample of the Serious Adverse Event Worksheet /electronic Serious Adverse Event Contingency Report Form. For EDC studies where the first notification of a Serious Adverse Event is reported to Amgen via the electronic Serious Adverse Event Contingency Report Form, the data must be entered into the EDC system when the system is again available.

The investigator must assess whether the serious adverse event is possibly related to talimogene laherparepvec. This relationship is indicated by a "yes" or "no" response to the question: "Is there a reasonable possibility that the event may have been caused by the investigational product"?

The investigator must assess whether the serious adverse event is possibly related to any study-mandated activity or procedure. This relationship is indicated by a “yes” or “no” response to the question: “Is there a reasonable possibility that the event may have been caused by a study activity/procedure”?

The investigator is expected to follow reported serious adverse events until stabilization or reversibility.

New information relating to a previously reported serious adverse event must be submitted to Amgen. All new information for serious adverse events must be sent to Amgen within 24 hours following knowledge of the new information. The investigator may be asked to provide additional follow-up information, which may include a discharge summary or extracts from the medical record. Information provided about the serious adverse event must be consistent with that recorded on the applicable CRF (eg, Adverse Event Summary eCRF).

If a subject is permanently withdrawn from protocol-required therapies because of a serious adverse event, this information must be submitted to Amgen.

Amgen will report serious adverse events and/or suspected unexpected serious adverse reactions as required to regulatory authorities, investigators/institutions, and IRBs/IECs in compliance with all reporting requirements according to local regulations and Good Clinical Practice (GCP).

The investigator is to notify the appropriate IRB/IEC of serious adverse events occurring at the site and other adverse event reports received from Amgen, in accordance with local procedures and statutes.

9.3 Pregnancy and Lactation Reporting

If a pregnancy occurs in a female subject, or female partner of a male subject, while the subject is taking protocol-required therapies, report the pregnancy to Amgen as specified below.

In addition to reporting any pregnancies occurring during the study, investigators should **report** pregnancies that occur after the last dose of talimogene laherparepvec through 3 months after the last dose of talimogene laherparepvec. The pregnancy should be reported to Amgen **Global Patient Safety** within 24 hours of the investigator’s knowledge of the event of a pregnancy. Report a pregnancy on the Pregnancy Notification Worksheet ([Appendix B](#)).

If a lactation case occurs while the female subject is taking protocol-required therapies report the lactation case to Amgen as specified below.

In addition to reporting a lactation case during the study, investigators should monitor for lactation cases that occur after the last dose of talimogene laherparepvec through 3 months after the last dose of talimogene laherparepvec.

Any lactation case should be reported to Amgen **Global Patient Safety** within 24 hours of the investigator's knowledge of event. Report a lactation case on the Lactation Notification Worksheet ([Appendix B](#)).

9.4 Reporting of Exposure to Talimogene Laherparepvec

If a household member, caregiver, or healthcare provider who has had close contact with the subject is suspected to have been exposed to talimogene laherparepvec (eg, have or who have had signs or symptoms suspected to be herpetic in origin or who have been accidentally exposed to talimogene laherparepvec), while the subject is taking talimogene laherparepvec, report the exposure to Amgen as specified below. In addition to reporting an unintended exposure case during the study treatment, investigators should monitor for potential exposure cases that occur after the last dose of talimogene laherparepvec through 30 (+ 7) days after the last dose of talimogene laherparepvec. **Please refer to your study specific documents for reporting details.**

Any potential or known unintended exposure should be reported to Amgen within 24 hours of the investigator's knowledge of the event of exposure. Amgen will seek to follow-up with the exposed individual, if necessary, to collect more information about the exposed individual contact with clinical trial subject, signs and/or symptoms related to the exposure, medical history, and/or outcome of the exposure. If the exposed individual is reporting signs or symptoms suspected to be related to talimogene laherparepvec exposure, the exposed individual may be asked to have a swab taken to evaluate for the presence of talimogene laherparepvec in the lesion, **within 3 days of the symptoms or signs occurring.**

10. STATISTICAL CONSIDERATIONS

10.1 Study Endpoints, Analysis Sets, and Covariates

10.1.1 Study Endpoints

10.1.1.1 Primary Endpoint

- Correlation between baseline intratumoral CD8+ cell density and objective response rate (ORR)

10.1.1.2 Secondary Endpoints

- Correlation between baseline intratumoral CD8+ cell density and durable response rate (DRR), and duration of response (DOR), and changes in tumor burden
- Correlation between changes in intratumoral CD8+ cell density during treatment and ORR, DRR, DOR, and changes in tumor burden
- Efficacy Endpoints: ORR, DOR, time to treatment failure (TTF), DRR, OS, and change in tumor burden during treatment
- Safety Endpoints: subject incidence of treatment-emergent and treatment-related adverse events (including all adverse events, grade ≥ 3 adverse events, serious adverse events, fatal adverse events, events of interest, adverse events requiring the discontinuation of study drug), clinically significant laboratory changes, and incidence of symptomatic herpetic lesions that are positive for talimogene laherparepvec

10.1.1.3 Exploratory Endpoints

- Correlation between the changes in the population of tumor specific cytotoxic T cells and immunoscore during treatment and clinical response
- Identification of other potential blood and tumor biomarkers which correlate with or predict clinical outcomes to talimogene laherparepvec

10.1.2 Analysis Sets

Safety Analysis Set: The safety analysis set will include all subjects who have received at least 1 dose of talimogene laherparepvec. The efficacy analysis and safety analysis will be performed on the safety analysis set.

Baseline Biomarker Analysis Set: The baseline biomarker analysis set will be defined separately for each baseline biomarker. The baseline biomarker analysis set includes all subjects who received at least 1 dose of talimogene laherparepvec and have the biomarker recorded at baseline. The correlation between a baseline biomarker and objective response rate, durable response rate, and duration of response will be conducted on the baseline biomarker analysis set.

Biomarker Evaluable Analysis Set: The biomarker evaluable analysis set will be defined separately for each biomarker. Lesions will be analyzed by injection status. The biomarker evaluable analysis set includes all subjects who received at least 1 dose of talimogene laherparepvec and have the biomarker recorded both at baseline and week 6. The correlation between biomarker changes during treatment and objective response rate, durable response rate, and duration of response will be conducted on the biomarker evaluable analysis set.

10.1.3 Covariates and Subgroups

The following covariates may be used to examine efficacy and safety in subgroups or in multivariate analyses:

- Region, if applicable
- Age at baseline: < 50, ≥ 50; < 65, ≥ 65; < 75, ≥ 75 years
- Disease stage at baseline: IIIB and IIIC vs IVM1a vs IVM1b vs IVM1c
- Baseline LDH ≤ ULN vs > ULN
- Sex (Female vs Male)
- ECOG Performance Status (0 vs 1)

10.2 Sample Size Considerations

All analyses will be descriptive with no formal hypothesis testing. The sample size was selected based on practical considerations. The primary objective of the study is to assess whether baseline intratumoral CD8+ cell density is correlated with the likelihood of response to talimogene laherparepvec. Analyses for the objective will focus on whether the response rate varies with baseline intratumoral CD8+ cell density. The functional manner in which the response rate may vary with the biomarker is unknown, therefore multiple functional relationships may be examined. It is assumed that 100 subjects (approximately 91% of the enrolled) will have an evaluable baseline intratumoral CD8+ cell density. The adequacy of the sample size was evaluated for one of several possible analyses that evaluates whether the response rate is positively correlated with a high baseline intratumoral CD8+ cell density where a low and high biomarker is defined as a value below versus at or above the sample median, respectively. A one-sided Fisher's Exact test will be performed at a 5% nominal level to explore the hypothesis that the response rate is equal regardless of baseline intratumoral CD8+ cell density. The overall ORR is assumed to be 26.4%. The power for the test will depend on the true response rates in the biomarker subgroups. Assuming the true response rate is 13.2% in the biomarker low subgroup, and 39.6% in the biomarker high subgroup, the power will be 88% to detect a positive association.

A secondary objective of this study is to estimate the objective response rate. Based on the analysis of the OPTiM study, the overall response rate for stage IIIB/C and IVM1c is assumed to be around 26.4% where, among responders, the probability of response onset after 12 months was < 5%. The expected exact 95% CIs for various true ORRs are listed in [Table 4](#). The expected width of the 95% CI is around 18% under these scenarios.

Table 4. Expected 95% Confidence Intervals by Various True ORRs

Subjects enrolled (N)	True	Expected 95% CI (width)
110	20%	13% - 29% (16%)
	30%	22% - 39% (18%)
	40%	31% - 50% (19%)
	50%	40% - 60% (19%)

Another secondary objective is to explore the correlation between changes in intratumoral CD8+ cell density during treatment and objective response rate. The primary focus will be on changes in tumor cell CD8+ density. It is assumed that 55 subjects (approximately 50% of all enrolled) will be evaluable with a pre- and on-treatment lesion biopsy that is sufficient to evaluate biomarker changes in uninjected lesions. In addition to correlating biomarker changes with objective response, Pearson's correlation coefficient (r) will also be estimated between the biomarker change and the maximum decrease in index lesions. With 55 evaluable subjects, a value of $r \leq 0.30$ will be rejected at a nominal 1-sided 5% significance level with an observed $r > 0.49$ for which the power will be $> 80\%$ given a true value for $r \geq 0.60$.

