11.1 General Principles

The main goals of this analysis are: (1) to better understand the distribution of intratumoral CD8+ cell density in the overall population and in subgroups; (2) to explore associations among baseline/change in intratumoral CD8+ cell density and efficacy endpoints; and (3) to explore the clinical potential utility of intratumoral CD8+ cell density cut-off values for patient selection.

Changes in intratumoral CD8+ cell density will be analyzed overall and separately for injected and uninjected lesions.

In principle, mean, standard deviation, median, first and third quartiles, minimum and maximum will be calculated for continuous variables; frequency count and percent will be calculated for binary and categorical variables. P-values will be used mainly as a descriptive measure suggesting comparative strength of association rather than to test hypotheses. Accordingly, nominal p-values will be generated with no adjustment for multiplicity. Analyses will be based on the Safety Analysis Set unless otherwise specified.

CCI

. The

following are some general principles which will be followed to handle such issues for efficacy analyses.

- It is desirable for subgroups to have 10 or more subjects for each dichotomization or categorization scheme, though judgment maybe applied.
- Analyses will be more carefully considered for robustness of results (e.g., K-M curves, model building, comparison between subgroups) when some subgroups have a small number of subjects and/or when there are few events for time-to-event endpoints..

CCI [REDACTED]
[REDACTED]
[REDACTED]
[REDACTED]
[REDACTED].

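### The one-sided Fisher test in Protocol 10.2 has an actual size of about 3%; Boschloo's exact test on the same table stays within 5% and adds about 2 to 4 points of power at no cost in subjects

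*Protocol*

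**What the plan says.** Protocol 10.2 describes one comparison for the primary endpoint for which it gives power. The inputs are:

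- Evaluable subjects: "It is assumed that 100 subjects (approximately 91% of the enrolled) will have an evaluable baseline intratumoral CD8+ cell density".
- Groups: "a low and high biomarker is defined as a value below versus at or above the sample median, respectively".
- Test: "A one-sided Fisher's Exact test will be performed at a 5% nominal level to explore the hypothesis that the response rate is equal".
- Effect: rates of 13.2% in the low group and 39.6% in the high group.
- Power at those rates: "the power will be 88% to detect a positive association".

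The same section limits the role of this test: "All analyses will be descriptive with no formal hypothesis testing". It presents the median split as one among several candidate analyses and says the sample size was chosen on practical grounds. SAP 11.1 agrees: "P-values will be used mainly as a descriptive measure suggesting comparative strength of association rather than to test hypotheses", and it makes no multiplicity adjustment.

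No visible text gives the actual type I error of the Fisher test or mentions an unconditional exact test. Most of SAP 11.4, which covers the association between CD8+ density and response, is blacked out, so this point rests on the protocol wording.

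**The concern.** A sample-median split fixes the two group sizes but leaves the number of responders random. Fisher's test treats that number as fixed as well. Its reference distribution is then coarse, and for most responder totals no table gives a p-value close to 5%. Averaged over the totals that can occur, the rejection probability under no association falls well short of the nominal level.

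Two things are at stake. The protocol describes the strength of this comparison through its power, and part of that power is given up by the choice of test. The SAP reads p-values as a measure of strength of association, and a conservative p-value understates that strength.

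**Working it through.** **Inputs (Protocol 10.2).** There are 100 evaluable subjects, giving 50 low and 50 high if there are no ties at the median. The true rates are 13.2% and 39.6%; their mean, (13.2 + 39.6)/2 = 26.4%, is the assumed overall ORR. The test is one-sided at 5%.

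**Step 1: Fisher's p-value.** With a responders among the 50 low and b among the 50 high, let t = a + b. Then p(a,b) = P(H ≥ b), where H is hypergeometric: t draws from 100 subjects, of whom 50 are high. Reject if p(a,b) ≤ 0.05.

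**Step 2: the plan's power.** Sum over all 51 × 51 tables: power = Σ Bin(a; 50, 0.132) × Bin(b; 50, 0.396) over tables with p(a,b) ≤ 0.05. The result is 0.8842, so the stated 88% reproduces.

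**Step 3: Fisher's actual size.** Use the same sum with one common rate π in both groups.
- At π = 0.264 the size is 0.0298.
- The maximum over a 4,000-point grid of π is 0.0332, near π = 0.34.
- At π = 0.264 the unused share of the nominal level is (5.00 − 2.98)/5.00 = 40%.

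**Step 4: Boschloo's test.** Keep p(a,b) as the statistic, and reject if p(a,b) ≤ c, where c is the largest value for which the maximum over π of the rejection probability is at most 0.05.
- c = 0.0698.
- The maximum size is 0.0486, and the size at π = 0.264 is 0.0470.
- The rejection region has 961 tables against Fisher's 925 and contains all of them, because c exceeds 0.05.
- Power at 13.2% v 39.6% is 0.9210, a gain of 92.1 − 88.4 = 3.7 points.

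Size at other common rates, 50 v 50:

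| Common rate | Fisher | Boschloo |
|---|---|---|
| 10% | 2.44% | 3.49% |
| 20% | 2.88% | 4.48% |
| 26.4% | 2.98% | 4.70% |
| 30% | 3.18% | 4.84% |
| 40% | 3.09% | 4.42% |
| 50% | 2.87% | 4.44% |

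**Step 5: other splits.** The 100 evaluable subjects are an assumption, so the calculation was repeated with the cut-off recalibrated for each pair of group sizes (low/high), at 13.2% v 39.6%:

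| Split | Fisher power | Boschloo power | Gain (points) |
|---|---|---|---|
| 45/45 | 85.2% | 88.8% | 3.6 |
| 48/48 | 87.8% | 90.9% | 3.1 |
| 49/50 | 89.0% | 90.9% | 1.9 |
| 50/50 | 88.4% | 92.1% | 3.7 |
| 50/51 | 89.0% | 92.0% | 3.0 |
| 55/55 | 91.7% | 93.5% | 1.8 |

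**Step 6: smaller effects with the same overall rate, 50 v 50.** At 15.0% v 37.8%, power goes from 77.4% to 83.3%. At 17.0% v 35.8%, it goes from 60.6% to 68.5%.

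**Step 7: an example of a changed reading.** With 26 responders split 17 high and 9 low, Fisher gives p = 0.055 and Boschloo p = 0.044.

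**The case against.** The case against acting on this is substantial, and most of it stands.

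- **No discrepancy in the plan.** A reader might infer from the 3% figure that the 88% is miscalculated or that the 5% level is breached. Neither is so. The 88% is correct for the test named, and the text says only that the level is nominal, which a conservative exact test satisfies.
- **No decision hangs on 5%.** The analysis is descriptive, one of several, and its power did not set the sample size. This limits the weight of the point. It does not remove it, because 10.2 still commits to performing the test and quotes its power.
- **Fisher's conservatism buys something.** Its guarantee also holds conditionally on the observed responder total, and Boschloo's does not. That is a real, if small, loss. The unconditional model fits here because nothing in the design fixes the responder total.
- **The guarantee is narrow.** A reader might take it to cover the study. It covers one test at one cut. Protocol 10.2 allows several functional relationships, 10.4.2 lists tests over all cut-points for secondary endpoints, and 10.3.1 plans an interim look at the same association. Boschloo's test would also give more nominal positives if there is no association: 4.70% against 2.98% at a common rate of 26.4%.
- **Reach.** It is tempting to say that the durable response comparison and other high-versus-low tests suffer the same loss. Protocol 10.4.2 speaks only of a test, and the relevant SAP text is largely blacked out, so no visible text says Fisher is used there.
- **The favourable point.** At exactly 50 v 50, Fisher would need 56 per group (92.2%) to match Boschloo, which is 12 more evaluable subjects. That should not be read as a general equivalence, because the gain at 49/50 is about half as large.

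**Conclusion.** The point holds as an efficiency gain. On the table described in Protocol 10.2, one-sided Fisher at a nominal 5% has a size of about 3%. Boschloo's test keeps the maximum size of this single test below 5%, never fails to reject when Fisher rejects, and adds about 2 to 4 points of power under the plan's assumed rates. The gain is 5.9 points at 15.0% v 37.8% (83.3 − 77.4).

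This rests on independent binomial responses in two groups of fixed size, on no ties at the median, and on evaluable numbers near 100. The plan's own arithmetic is sound. The point concerns the choice between two valid tests for one exploratory analysis. Severity: CONSIDER.

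**What to change.** In Protocol 10.2, before any results are seen:

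1. Name a one-sided Boschloo exact unconditional test for the median-split ORR comparison, keeping the 5% nominal level.
2. Restate the power as about 92% assuming 50 v 50, and note that it is about 91% at 49/50.
3. Report Fisher's p-value alongside, and say that the 5% bound is unconditional and applies to this one test.
4. If Fisher's test is also planned for other low-versus-high 2x2 comparisons, the same substitution can be made there.

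The cost is a change of wording, matched in the SAP, and a standard software call. No further subjects, biopsies or data are needed.
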